#### **4.2 Handling of Dropouts**

Not applicable.

#### **4.3 Handling of Missing Data**

Missing data will not be imputed for statistical analysis.

#### **4.4 Interim Analyses and Data Monitoring**

Not applicable.

#### **4.5 Data Rules**

Baseline value for laboratory measurements and ECOG performance status are the last non-missing values documented before or on the day of first study medication administration in the STEP study.

In this study, adverse events (AEs) ongoing from previous study could also be documented in addition to newly occurring AEs. Since the STEP data are not combined with data from the feeder trials, the start and stop dates of sorafenib treatment in the feeder trial are not available and it cannot be derived if the ongoing AEs are treatment-emergent or not. The ongoing AEs will therefore be analyzed separately and not termed 'treatment-emergent'. AEs in STEP are considered as treatment-emergent, if they start or worsen from enrolment date in STEP and up to 30 days after the last sorafenib dose. New non-treatment emergent AEs are those that start later than 30 days after last sorafenib treatment.

The investigator should document the AE start date and additionally tick if an AE was ongoing from previous study or not. The assignment if an AE is ongoing or new will be primarily based on the AE start date and will be done according to the following rules:

- Any AE documented on or after enrolment date in STEP will be considered as new.
- Any AE with start date before STEP enrolment date will be considered as ongoing.
- In case the AE start is partially missing (i.e. day and/or month are missing), the date will be imputed as specified below.
- If the AE start date is completely missing, the answer to the question 'Ongoing from previous study' will be used – 'yes' indicates the AE is ongoing, 'No' indicates the AE is new.

The following imputation will be used for partially missing AE start date, whenever it is necessary to assign the AE to the 'ongoing' or 'new' category:

- If only the day is missing, the first of the month will be used, except if the start month/year are equal to enrolment month/year, then the start day of enrolment will be used.
- If day and month are missing, then 1st of July will be used, except if the start year is equal to the enrolment year, then the start day/month of enrolment will be used.

#### **4.6 Blind Review**

The results of the final data assessment will be documented in the validity findings and assignment to analysis sets. Any changes to the statistical analysis prompted by the results of the review of study data will be documented in an amendment and, if applicable, in a supplement to this SAP.

### **5. Analysis Sets**

#### **5.1 Assignment of analysis sets**

Final decisions regarding the assignment of subjects to analysis sets will be made during the review of the study data and documented in the validity findings and analysis sets (see Section 4.6).

##### **Full analysis set (FAS) = All enrolled subjects**

All subjects who signed informed consent for STEP are contained in the FAS. This analysis set will be used for disposition tables and subject data listings.

##### **Safety analysis set (SAF)**

The population for safety analysis will be comprised of all subjects who received at least one dose of study medication. The SAF will be used for the analyses of the population characteristics and baseline variables, treatment duration, ECOG performance status, and all safety parameters.

### **6. Statistical Methodology**

#### **6.1 Population characteristics**

The number and percentage of subjects enrolled will be displayed by feeder trial. The number and percentage of subjects enrolled as well as the reason for termination of treatment will be summarized.

Baseline characteristics and demographics (age, sex, race, diagnosis of cancer, and ECOG performance status) will be summarized for the time point entering this study 12311; as documented in 12311. Age will also be categorized as 15-17, 18-64, 65-74, 75-84,  $\geq 85$  years, as applicable.

## 6.2 Efficacy

Not applicable.

## 6.3 Pharmacokinetics/pharmacodynamics

Not applicable.

## 6.4 Safety

Descriptive statistics will be calculated for the treatment duration. Duration of study treatment within STEP will be calculated in days as the date of the last dose of any study treatment – date of the first dose of any study treatment + 1. Duration in months will be presented in months, calculated by dividing days by 30.4. In addition to the descriptive statistics referenced in section 4.1, the sum of all treatment durations will also be calculated.

Adverse Events (AEs) will be coded according to the most recent version of the Medical Dictionary for Regulatory Activities (MedDRA). AE grading will be documented using version 3.0 of the National Cancer Institute (NCI) Common Terminology Criteria for Adverse Events (CTCAE).

In STEP, AEs ongoing from previous study as well as new AEs occurring during STEP were collected. AEs will be classified as ‘ongoing AE’, ‘new treatment-emergent AE’ or ‘new non treatment-emergent AEs after 30 days after last sorafenib dose’ (see Section 4.5). Tables will be created for ongoing AE, new treatment-emergent AE, and the combination of both. New non treatment-emergent AEs after 30 days after last sorafenib dose will only be listed.

AEs will be summarized by counts and incidence proportions, and grouped by MedDRA system organ class, MedDRA preferred term, and worst CTCAE grade, for the following:

- New TEAEs in STEP:
  - TEAE
  - Drug-related TEAE
  - TEAE leading to dose reduction
  - Drug-related TEAE leading to dose reduction
  - TEAE leading to dose interruption
  - Drug-related TEAE leading to dose interruption
  - TEAE leading to drug discontinuation
  - Drug-related TEAE leading to drug discontinuation
  - TESAE
  - Drug-related TESAE
  - TEAEs leading to death
  - Drug-related TEAEs leading to death
- Ongoing AEs from feeder studies:

- AEs
- Drug-related AEs
- SAEs
- Drug-related SAEs
- All AEs in STEP (ongoing AEs from feeder studies + new TEAEs in STEP)
  - AEs
  - Drug-related AEs
  - SAEs
  - Drug-related SAEs

The numbers of deaths and the primary cause of death (as reported by the investigator) will be tabulated and listed.

Hematology and blood chemistry values will be summarized according to their worst CTCAE grade, where applicable. Hematology and blood chemistry values will be graded based on the applicable laboratory threshold values outlined in NCI CTCAE version 3.0.

Individual time courses of ECOG performance status will be displayed graphically.

Frequencies of the ECOG performance status categories will be summarized for baseline and per 6-month time interval, using the last value per 6-month time interval.

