7.3.6 Adverse Event Documentation

All treatment related adverse events or adverse events NCI-CTCAE Version 3.0 Grade 3 or higher (regardless of attribution) occurring after the subject has signed the informed consent must be fully recorded in the subject's case record form.

yyy Documentation must be supported by an entry in the subject's file. A laboratory test abnormality considered clinically relevant, eg, causing the subject to withdraw from the study, requirement treatment or causing apparent clinical manifestations, or judged relevant by the investigator, should be reported as an adverse event. Each event should be described in detail along with start and stop dates, severity, relationship to investigational product, action taken and outcome.

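### SAP 6.4 plans tables of AEs leading to dose reduction, interruption or discontinuation for new TEAEs only, so an unworsened carried-over AE that leads to such an action in STEP is in none of them

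*SAP*

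**What the plan says.** SAP 6.4 itemises the AE tables in three blocks. The block for new treatment-emergent events contains "TEAE leading to dose reduction", "TEAE leading to dose interruption", the corresponding discontinuation table and the corresponding death table, each for all events and for drug-related events (for example "Drug-related TEAE leading to drug discontinuation" and "Drug-related TEAEs leading to death"). The block for events ongoing from the feeder studies, and the block headed "All AEs in STEP (ongoing AEs from feeder studies + new TEAEs in STEP)", each list four tables only: AEs, drug-related AEs, SAEs and drug-related SAEs.

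SAP 4.5 decides which block an event belongs to. Its operational rule is "Any AE with start date before STEP enrolment date will be considered as ongoing". The same section also defines an AE as treatment-emergent if it begins or gets worse between STEP enrolment and 30 days after the last sorafenib dose.

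Two other outputs bear on the point. SAP 6.1 says that "the reason for termination of treatment will be summarized". SAP 6.4 plans a table and listing of deaths with the investigator's primary cause. Neither depends on when the AE began. Protocol 7.3.6 requires each recorded event to be described with "severity, relationship to investigational product, action taken and outcome".

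**The concern.** Safety is the only objective of STEP that is analysed; efficacy is not applicable in either document. Every patient enters already taking sorafenib, Protocol 4.1 has ongoing AEs recorded in the STEP CRF at entry, and Protocol 4.5.1 foresees patients arriving on a dose already reduced for an AE. Carried-over toxicity is therefore a foreseeable reason for changing or stopping treatment during STEP.

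SAP 4.5 keeps ongoing events apart because feeder-trial treatment dates are unavailable, so it cannot be derived whether those events were treatment-emergent. That reason concerns onset. It does not explain why an action taken on STEP treatment during STEP should be left out of the action tables. At stake is whether the AE-related dose-modification and discontinuation rates in the report cover all such actions in STEP, or only those attached to events that began after enrolment.

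**Working it through.** **1. Count the planned tables by block (SAP 6.4).**

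| Block | All tables | Reduction, interruption, discontinuation | Death |
|---|---|---|---|
| New TEAEs | 12 | 6 | 2 |
| Ongoing AEs | 4 | 0 | 0 |
| All AEs combined | 4 | 0 | 0 |

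So there are 8 action or death tables for new TEAEs and none for the other two classes.

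**2. Follow a carried-over event through SAP 4.5.**

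- *It does not worsen, but leads to an action in STEP.* It is ongoing under the start-date rule, and it is not treatment-emergent under the definition either. It is in no action table on any reading.
- *It worsens and leads to an action in STEP.* Under the start-date rule it is ongoing and is lost. Under the definition that includes worsening it is treatment-emergent and is counted. The SAP does not say which rule governs.

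**3. Look for another planned output that would show the outcome.**

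- *Dose reduction or interruption:* none. SAP 6.4 summarises treatment duration but plans no table of dose changes. The subject listings under SAP 5.1 may show single cases.
- *Discontinuation:* the reason-for-termination summary in SAP 6.1 covers all patients whatever the AE onset. Term, grade and relatedness are not given there.
- *Death:* the deaths table in SAP 6.4 covers all deaths with primary cause. The breakdown by AE grade and relatedness is not given there.

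**4. Size per omitted patient.** The 26 feeder-trial counts in SAP Table 1–1 sum to 206, which reproduces the stated total. SAP 4.1 says one patient received sorafenib plus erlotinib and that this patient's safety data will only be listed. Assuming every other patient was dosed, the monotherapy denominator is 206 − 1 = 205. A patient whose only qualifying event for an action is a carried-over AE lowers the overall incidence for that action by 100 / 205 = 0.49 percentage points.

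The documents give no number of such patients. Over an assumed range:

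| Patients omitted (assumed) | Loss, percentage points |
|---|---|
| 0 | 0 |
| 2 | 2/205 = 1.0 |
| 4 | 4/205 = 2.0 |
| 10 | 10/205 = 4.9 |
| 20 | 20/205 = 9.8 |

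A patient who also has a new TEAE leading to the same action is still counted in the overall row. Only the preferred-term row for the carried-over event is then short.

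**The case against.** The strongest points on the other side are these.

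- **The gap is narrow.** Protocol Tables 4–1 and 4–2 call for no dose change at Grade 0–2, so an event at those grades must worsen before the tables require action, and a worsened event may count as treatment-emergent. For skin toxicity, Table 4–4 works by successive appearances, and a reappearance with its own start date in STEP is new. This limits the number of cases but does not remove them. Footnotes to Tables 4–1 and 4–2 provide for discontinuation when there is no recovery after a 30-day delay, which is triggered by persistence. Protocol 4.3 also requires stopping for unacceptable toxicity without setting a grade.
- **A reader might infer that every action caused by a carried-over AE is lost.** The documents do not support that, because the worsening clause in SAP 4.5 could bring worsened events into the action tables.
- **A reader might infer that deaths and discontinuations go unreported.** They do not. Both are summarised whatever the AE onset. An event that was not fatal at enrolment and later causes death has also worsened, so it is treatment-emergent under the SAP 4.5 definition.
- **A reader might see a contradiction between the termination summary and the discontinuation table.** They are differently labelled, and SAP 5.1 assigns disposition to all enrolled subjects and safety to dosed subjects. The documents do not give the CRF categories for termination, so an AE category is itself an assumption. A difference would need a note, but it is not an inconsistency in the plan.
- **Added tables could overstate.** The action recorded for a carried-over AE may have been taken in the feeder trial, and Protocol 7.3.6 does not ask for the date of the action. This stands and shapes the fix. It is weakest for discontinuation, since stopping STEP treatment can only happen in STEP. For dose changes, Protocol 4.6.2 puts the sorafenib start and stop dates and the dose in the CRF, which allows a check.
- **SAP 6.4 says tables will be made for ongoing events, new events and both together.** That could be read as covering the action tables, but the itemised list gives them for one class only.

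**Conclusion.** The omission is definite in structure and of unknown size. A carried-over AE that does not worsen but leads to a dose reduction, interruption or discontinuation in STEP is in no planned action table. For reductions and interruptions no other planned table shows it. For discontinuations and deaths what is lost is detail by AE, not the outcome.

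It is tempting to say that tolerability in STEP is understated. The documents support only that the AE-related rates can be understated and that this omission cannot overstate them. The effect is about 0.49 percentage points per omitted patient, given 205 dosed monotherapy patients, and the number omitted may be zero. Whether worsened carried-over events add to it depends on which SAP 4.5 rule is applied. The change is worth making because it is cheap and concerns the only objective that is analysed.

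**What to change.** In SAP 6.4, add to the combined block tables of AEs leading to dose reduction, dose interruption and drug discontinuation, each for all and for drug-related events: six tables, or eight if death is included. Split the rows by ongoing versus new. Count only actions on or after the first STEP dose, verified against the CRF dosing dates and doses, and list separately any case where the action cannot be dated to STEP. Present these tables beside the TEAE tables and explain any difference from the reason-for-termination summary.

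In SAP 4.5, state whether the start-date rule or the worsening clause governs a carried-over AE that worsens in STEP.

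The cost is SAP wording, a few more standard outputs and a dosing-record check for carried-over AEs with a recorded action. The figures may be slightly less favourable. No new data collection is proposed.

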Study 12444 (RESILIENCE).^{bb} The patient should be evaluated according to Good Medical Practices as well as local therapeutic and diagnostic standards. The patients should be evaluated by a study physician for safety at least once every 8 weeks and more frequently as needed. The protocol allows for a ± 7 days window when scheduling any visit. Physicians can choose to continue to see the patients every 8 weeks in a face to face visit. At least every other visit must be a mandatory on site visit for examination and drug dispensing, with the other visit being either in person or as a phone call. It is at the discretion of the investigator based on the patient's current condition and adverse event profile to determine if the next visit will be performed on site or as a phone visit. Any scheduled phone visit is mandatory and it will be at the discretion of the investigator to decide if that phone visit is sufficient. If the patient needs a physical examination, the visit will be performed on site. If the investigator feels the patient is stable with no new safety concerns nor new AEs in between visits, a phone call with labs, ECOG and review of AEs would be enough^{cc}. Once every 8 weeks^{cc} safety evaluations include vital signs (ie, heart rate, blood pressure, temperature) only when the visit is on site, **Eastern Cooperative Oncology Group (ECOG) performance status**, laboratory evaluations may be performed by local accredited lab which need to have PI signoff within a week of drawing^{dd} (hematology, ALT, AST, lipase and amylase, PT-INR as applicable for anticoagulated patients) and a review of any new or ongoing adverse event or concomitant medications as well as study medication taken during the visit interval. All adverse events, laboratory data, **ECOG performance status and survival status (dead or alive and date of death or date of last contact)**,^{ee} as well as End of Treatment information and study medication taken must be clearly and accurately recorded in the Case Report Form provided. All other data, including but not limited to, vital signs, concomitant

bb: Information on the erlotinib and capecitabine formulations was added under Amendment 3. See Section 10.3, Modification 5. Reference to capecitabine was removed with Amendment 8. See Section 10.6.4, Modification 4.

cc Safety follow-up adjusted by Amendment 7 to lessen the travel burden on patients. See Section 10.5.3, Modification 3.

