 - ***Survival status***

End of treatment

In addition to the above parameters, please record the following in the CRF and source documents:

- The reason for termination
- Date of last dose

hhhh: Language specific to the recording of adverse event information in Japan was added under Amendment 3. See Section 10.3, Modification 2. Language specific to the recording of adverse event information in Japan was removed with Amendment 8. See Section 10.6.8, Modification 8.

iiii: The bullet for other variables and the corresponding sub-bullets for ECOG performance status and survival were added in Amendment 3. See Section 10.3, Modification 1 and Modification 2.

- ***Survival status (dead or alive and date of death or date of last contact)***^{jjjj}

Follow-up period

All subjects will be followed until 30 days after the last dose of study drug.^{kkkk /lll}

If a patient discontinues due to an adverse event or clinical laboratory abnormality, the patient should be followed until the event resolves, the patient stabilized, or 30 days, whichever is shorter. If a patient dies within 30 days of the last dose of study medication, the SAE complementary form should be completed and forwarded to Bayer Global Drug Safety.^{mmmm}

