 - Treatment related event – all CTC grades
 - Any CTC Grade 3 or 4 event (regardless of attribution)
 - Any Serious Adverse Event (regardless of attribution)
- Study medication (date dispensed and returned, number of tablets dispensed and returned)
- Laboratory Assessments

End of treatment

In addition to the above parameters, please record the following in the CRF and source documents:

- The reason for termination
- Date of last dose
- ~~Date of death, if applicable~~

Follow up period

If a patient discontinues due to an adverse event or clinical laboratory abnormality, the patient should be followed until the event resolves, the patient stabilized, or 30 days, whichever is shorter.....

New text:

Observations and Measurements

Once enrolled in this program.....

- Assessment of Adverse Events
 - Treatment related event – all CTC grades
 - Any CTC Grade 3 or 4 event (regardless of attribution)
 - Study Sites in Japan: In accordance with Japanese regulatory requirements ALL adverse events regardless of NCI-CTCAE grade and regardless of attribution are to be recorded.**
 - Any Serious Adverse Event (regardless of attribution)
- Study medication (date dispensed and returned, number of tablets dispensed and returned)
- Laboratory Assessments
- Other variables
 - ECOG performance status
 - Survival status

End of treatment

In addition to the above parameters, please record the following in the CRF and source documents:

- The reason for termination
- Date of last dose
- Survival status (dead or alive and date of death or date of last contact)

Follow up period

All subjects will be followed for survival. Assessment of survival status will be performed approximately every 3 months in the follow-up period.

If a patient discontinues due to an adverse event or clinical laboratory abnormality, the patient should be followed until the event resolves, the patient stabilized, or 30 days, whichever is shorter.....

Section 4.6.4, Drug Concentration Measurements

Old text:

~~**Section 4.6.4, Drug Concentration Measurements**~~

~~Not applicable~~

New text:

There is no new text; this section was deleted

Section 5.1, Ethics Committee (EC) or Institutional Review Board (IRB)

Old text:

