10.5.5 Modification 5: Follow-up period changed

Description of modification to the study objectives:

FU period was changed from until survival to until 30 days after last dose of study drug. Overall survival is removed from the objective.

Rationale:

This would allow some sites with only patients in survival follow-up for years to close, and to minimize burden to patients and to enable better compliance at sites.

List of affected sections:

Sections [4.6.3](#), [11.1](#)

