11.1 Study Flow Chart

Activity ^{zzzz}	Visit 1	Minimum Every 8 weeks (±7 days) ^{aaaaa}	End of Treatment
Demography ^{a, b}	X		
Pregnancy Test	X		
Vital signs	X	X	X
ECOG performance ^a	X	X	X
Survival status (dead or alive, date of death or date of last contact, as applicable) ^{bbbb}		X	X ^d
Adverse events ^a			
All treatment related	X	X	X
All Grade 3 or higher regardless of attribution	X	X	X
All serious adverse events	X	X	X
Laboratory evaluations ^a			
Hematology (Hgb, RBC, WBC, platelets, differential)	X	X	X
CBC (ALT, AST, amylase, lipase)	X	X	X
PT-INR ^c			
Dispense/return sorafenib (and capecitabine if applicable) ^{cccc} ^{dddd} ^a	X	X	X
Reason for termination of treatment ^a			X
Concomitant medications	X	X	X

a Record these data in the CRF and source documents.

b Includes originating study number, patient number and date of first sorafenib dose in originating study.

c For anticoagulated patients only

d The long term follow up period is until 30 days after last dose of study drug.^{eeee} ^{ffff}

^{zzzz}: The text row regarding date of death was deleted in Amendment 3. See Section 10.3, Modification 6.

^{aaaaa} The visit window has been modified by Amendment 7. See Section 10.5.3, Modification 3.

^{bbbb}: The text row concerning survival was added in Amendment 3. See Section 10.3, Modification 1.

^{cccc} Reference to erlotinib removed since none of the subjects that transferred into this study were assigned to erlotinib from study 12917. See Section 10.4, Modification 2.

^{dddd}: Participation of subjects from the SEARCH trial (Study 12917) or the RESILIENCE trial (Study 12444) was added under Amendment 3. See Section 10.3, Modification 5

^{eeee}: The table footnote regarding assessment of survival was added in Amendment 3. See Section 10.3, Modification 1.

^{ffff} The table footnote was revised to change the FU period to until 30 days after last dose of study drug in Amendment 7. See Section 10.5.5, Modification 5.

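### Does the death table in SAP 6.4 need a stated time window and data source?

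*SAP*

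**What the plan says.** SAP 6.4 covers deaths in one sentence: "The numbers of deaths and the primary cause of death (as reported by the investigator) will be tabulated and listed". No time limits and no CRF page are given.

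For adverse events the SAP is explicit. SAP 4.5 treats events as treatment-emergent "if they start or worsen from enrolment date in STEP and up to 30 days after the last sorafenib dose", and SAP 6.4 adds: "New non treatment-emergent AEs after 30 days after last sorafenib dose will only be listed". SAP 6.4 also plans tables of treatment-emergent events leading to death, overall and drug-related. The safety analysis set in SAP 5.1 fixes who is counted, not when.

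The current follow-up rule in Protocol 4.6.3 is: "All subjects will be followed until 30 days after the last dose of study drug". Footnote d of the flow chart in Protocol 11.1 agrees: "The long term follow up period is until 30 days after last dose of study drug". The survival item in the CRF is described in Protocol 4.1 as "survival status (dead or alive and date of death or date of last contact". Protocol 4.3 asks for cause and date of death on the End of Treatment page. For a death during the trial or within 30 days of last dose, it also asks for the SAE form and the Adverse Event page.

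**The concern.** Survival follow-up was not constant over the life of the study. The Amendment 3 text, reproduced in Protocol 10.3.2, read: "All subjects will be followed for survival. Assessment of survival status will be performed approximately every 3 months in the follow-up period". Amendment 7 withdrew this, and one reason given in Protocol 10.5.5 was: "This would allow some sites with only patients in survival follow-up for years to close". Late follow-up therefore did take place, and the final database may hold deaths well beyond 30 days after last dose for some patients.

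Read literally, the SAP sentence would pool deaths on or shortly after treatment with such late deaths. The total would then depend partly on when a patient stopped treatment relative to two amendment dates, and the late deaths might have no recorded cause. It could be read neither as deaths on sorafenib nor as survival. Safety is the only stated objective besides continued access, and deaths are a core safety result, so the question deserves a check.

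**Working it through.** The plan gives no figure to reproduce. The check compares passages, with some date arithmetic.

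**1. How deaths were collected over time.** The amendment log is used here only as a history of data collection.

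| Period | What the protocol asked for |
|---|---|
| 5 July 2007 to March 2012 | Date of death at End of Treatment and in the CRF safety variables (superseded text in 10.3.2); no survival schedule, though survival information might be reported later |
| March 2012 to 15 May 2018 | Survival status about every 3 months, no end stated |
| From 15 May 2018 | Follow-up to 30 days after last dose |

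The day in March 2012 is not given. From 1 March 2012 to 15 May 2018 is 2266 days, and 2266 / 365.25 = 6.2 years. From 31 March it is 2236 days, and 2236 / 365.25 = 6.1 years. This is calendar time under one rule. It does not measure how many late deaths exist, because the documents give no treatment stop dates. Late deaths could also have been noted before Amendment 3, without a schedule.

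**2. Which records can feed a table of deaths with primary cause.**
- End of Treatment page: cause and date (Protocol 4.3).
- SAE form and Adverse Event page: deaths during the trial or within 30 days of last dose (Protocol 4.3).
- Survival item: status and date; no cause is described (Protocol 4.1 and 4.6.3).

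A table that reports investigator-assessed cause draws naturally on the first two. Amendment 7 (Protocol 10.5.2) removed overall survival because those data were not used in analyses, and SAP 6.2 lists no efficacy analysis. Late deaths are still not shown to be exactly nil. Protocol 7.3.5 and 7.4 follow each serious event to resolution or stabilization, so a death after day 30 can arrive through SAE records.

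**3. What the SAP already reports within the window.** A death no later than 30 days after last dose must come from an event that began no later than that. It therefore meets the upper limit of the treatment-emergent definition. Protocol 4.3 requires it on the Adverse Event page. Protocol 7.3.1 has serious signs and symptoms of progression, including fatal ones, reported as SAEs, so deaths from progression are not lost. The tables of treatment-emergent events leading to death should therefore contain essentially all deaths in the window. They can also include a death after day 30 if the fatal event began earlier.

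**4. Size if late survival records did enter.** This needs assumptions that are not in the documents. Take all 206 patients in SAP Table 1–1 as treated, 10% dying within 30 days of last dose, 30% to 60% of the rest dying later, and 25% to 75% of those late deaths captured.
- Within 30 days: 206 × 0.10 = 20.6.
- Late and captured, low: 206 × 0.90 × 0.30 × 0.25 = 13.9; total 34.5.
- Late and captured, high: 206 × 0.90 × 0.60 × 0.75 = 83.4; total 104.0.

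The total would be sensitive to the window if those records were used. The inputs are invented, and the illustration says nothing about whether the records would be used.

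**The case for a change.** The strongest case for a change is that the SAP's authors saw this issue for adverse events and wrote a 30-day rule, but wrote none for deaths. The source is also not beyond doubt: the End of Treatment list in Protocol 4.6.3 names survival status rather than cause, so the same kind of item carried death dates both at End of Treatment and during follow-up. The tables of fatal treatment-emergent events select on onset of the event, not on date of death, and do not define the separate overall count. The company table standards cited in SAP 4.1 might set a window, but their content is not in the documents. One or two sentences would settle the matter with no new data.

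Most of this stands as description. SAP 6.4 has no window and no named source, and the unseen standards cannot be relied on. What does not follow is that the reported safety result would mislead. The onset rule captures deaths inside the window, and any extra deaths it admits come from events that began within it. One loose edge remains: SAP 4.5 classes events as ongoing or new by start date, so a fatal worsening of an event carried over from a feeder trial could be filed as ongoing. A window on the overall death table would not change that classification.

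**Conclusion.** No change to the plan is needed. The gap is real but is one of missing detail. The overall count could include some incompletely ascertained late deaths, possibly without a cause. Their number cannot be derived from the documents and may be small or nil. The result that matters for safety, deaths tied to treatment, is already largely supplied by the tables of treatment-emergent events leading to death, and all deaths are listed. No test, comparison or decision rule depends on the total.

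This rests on three assumptions: that sites complete the Adverse Event page for deaths as Protocol 4.3 requires; that the analyst takes cause of death from where the protocol places it; and that any later deaths are separated by date, as the SAP already does for late adverse events. An analyst working from a protocol whose follow-up ends at 30 days would ordinarily do this. Writing the window and source into SAP 6.4 would be harmless tidying, but it would mainly record what would be done anyway.
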